6. AIMS OF THE STUDY

Our proposed study evaluates the measurement of proteinuria in women with suspected preeclampsia (PE). This includes women with gestational hypertension $\geq 140/90$ mmHg and \geq Trace proteinuria on automated dipstick analysis.

Primary Objectives:

1. To evaluate the diagnostic accuracy of quantitative assessments of SPCr and SACr (index tests) at different thresholds in predicting severe PE compared to 24 hour urine protein measurement

Secondary Objectives:

2. To assess the accuracy of point of care assessments of SPCr and SACr at different thresholds in diagnosing PE compared to 24 hour urine protein measurement
3. To identify the laboratory assay method of 24 hour proteinuria that is most accurate in the assessment of PE
4. To estimate the accuracy of both quantitative and point of care assessments of SPCr and SACr at different thresholds in predicting adverse fetal outcomes
5. To estimate the diagnostic utility of SPCr or SACr as a potential replacement for 24 hour protein estimation by developing a decision analytic model
6. To assess the cost effectiveness using cost per correct diagnosis and cost per adverse outcome predicted as key measures

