8. HEALTH TECHNOLOGIES BEING ASSESSED

8.1 Index tests

Laboratory quantitative tests (Laboratory SPCr and SACr)

Urinary protein will be measured using a benzethonium chloride turbidimetric method in all recruiting hospitals. The reagent acts as a denaturing agent causing the formation of a fine suspension in the reaction mixture. The analytical range for the Benzethonium chloride assay is 68 to 2000 mg/L and the day-to-day precision is 1.4 – 3.0%.

The SACr will be measured using an automated chemistry analyzer. Albumin is measured using an immunoturbidimetric immunoassay. The analytical range of the assay is 5 to 500 mg/L, and the day-to-day precision is within the range 2.5 – 5.0%. The analytical range of the assay is 0.3 to 44.2 mmol/L and the day-to-day precision is between 1.5 – 3.0%.

The urine creatinine will be measured using an enzymatic reaction, in which creatininase hydrolyses creatinine to creatine, which is itself hydrolysed by creatinase to sarcosine and urea. The analytical range of the assay for SPCr is 0.3 to 44.2 mmol/L and the day-to-day precision is between 1.5 – 3.0%.

Point of Care tests (Semi quantitative reagent strip SACr).

The dipstick test for ACR comprises two test pads, the colours formed in the presence of albumin and creatinine being read using a reflectance meter; the system provides a semi-quantitative result. The detection of albumin is based on binding of Bis (3',3''-diiodo-4',4''-hydroxy-5',5''-dinitrophenyl)-3,4,5,6-tetrabromosulfonephthalein (DIDNTB) at pH 1.5. It has been shown to be specific for the detection of albumin. The detection limit of the method is 0.9 mmol/L (10 mg/dl). The ACR is reported as one of the following ranges in conventional units (mg/g): <30, 30-300; or >300; or one of the following ranges in SI units (mg/mmol): <3.4, 3.4-33.9, or >33.9.

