8.2 Comparative tests (24 hour proteinuria and 24 hour albuminuria)

The measurement of the total protein concentration in urine is difficult for several reasons. The quantity of total protein is much lower in urine than in serum and there is large sample-sample variation, as well as interference from non-protein substances [18]. There are a number of different assays for measuring urinary total protein. Most laboratories in the UK currently use turbidimetric or colorimetric assays. The two most common methods employed are the benzethonium chloride and pyrogallol methods; for this reason we plan to study the variation of performance of these two methods to give an overview of the variation found between laboratories. Either a protein or albumin concentration or a fully quantitative SPCr or SACr can be reported.

Total Protein will be measured using a benzethonium chloride turbidimetric method in our secondary reference lab to explore inter-laboratory variation from the recruiting centres. Additionally, total protein will be measured using the Pyrogallol Red method (Sigma, Saint Louis, Missouri, USA) on a Cobas Mira Plus (Roche Diagnostics, Basel, Switzerland). In the assay, a pyrogallol red-molybdate complex binds to basic amino acid groups of protein molecules causing an increase in absorbance measured at 600 nm. The analytical range of the assay is stated by the manufacturer to be 10 to 2000 mg/L urinary total protein.

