9. STUDY CONDUCT

All eligible women will be invited to participate at each site. Women will be given trial information by the research midwife and a Participant Information Sheet (PIS) to keep, and then subsequently recruited following obtaining written consent.

As part of routine clinical care women are asked to provide a urine sample for protein analysis. In those women who consent to taking part in this study, an aliquot of the spot urine sample will be collected and stored at -80°C. This spot urine will then be sent for a laboratory SPCr. Clinical management will be determined at this point based on the automated urine dipstick result and SPCr (as per routine practice). Women will then be asked to collect a 24 hour urine sample as either an in-patient or outpatient, dependent on the clinical care plan (as per NICE CG107) [5]. Those women with trace proteinuria and a SPCr <30mg/mmol (i.e. without clinical PE) will collect as an outpatient and those with a SPCr of >30 mg/mmol (i.e. with a clinical diagnosis of PE) will collect as an in-patient. An aliquot of this 24-hour urine sample will be stored at -80°C for secondary analysis. Clinical management will be determined from the automated dipstick, the local laboratory SPCr and /or the local laboratory 24 hour urine collection performed locally.

Immediately prior to delivery, a further spot sample of urine will be taken and stored for later analysis. This will allow the maximum proteinuria level to be calculated as well as the increase in proteinuria from initial presentation.

Women will be followed up until 6 weeks postnatal when their blood pressure and proteinuria results (from either hospital / primary care clinics) will confirm their pregnancy diagnosis. At this point a detailed collection of outcome data will be performed by the research midwife. Data will be abstracted from the hospital records for the maternal and neonatal outcomes at birth and discharge home.

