The aliquots of urine will be sent in batches for secondary analysis at East Kent Hospitals Trust of 24-hour total albumin excretion by 2 different assays. The spot urine sample will also be tested using point of care testing for SPCr (semi-quantitative dipstick); POC SACr (semi-quantitative dipstick); and POC SACr (fully quantitative test). All data will be entered into a clinical data management software package supplied by MedSciNet configured to allow web-based entry from each of the seven clinical sites as well as the secondary analysis laboratory.

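### Section 9 assigns the central two-assay analysis of the 24-hour aliquots to albumin, whereas section 8.2 and objective 3 require two assays of total protein

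*Protocol*

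**What the plan says.** Objective 3 (section 6) reads: "To identify the laboratory assay method of 24 hour proteinuria that is most accurate in the assessment of PE". The analyte is protein in a 24-hour collection, and the comparison is between laboratory assays.

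Section 8.2 sets out how that comparison is made. It names benzethonium chloride and pyrogallol as the two methods most used in UK laboratories and says that the variation between them will be studied. The secondary reference laboratory measures total protein by benzethonium chloride, and then: "Additionally, total protein will be measured using the Pyrogallol Red method".

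Section 9 is the operative account of what happens to each sample. An aliquot of the 24-hour urine is frozen for secondary analysis. Aliquots then go in batches for analysis "of 24-hour total albumin excretion by 2 different assays". The text of section 9 mentions no central total-protein measurement.

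For the spot urine, section 8.1 lists "Laboratory quantitative tests (Laboratory SPCr and SACr)" as index tests. Section 9 says "This spot urine will then be sent for a laboratory SPCr" and adds point-of-care tests, among them "POC SACr (semi-quantitative dipstick); and POC SACr (fully quantitative test)". It does not say where laboratory SACr is run, or on which sample.

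**The concern.** A laboratory that receives batches of frozen aliquots works from a list of tests per sample, and section 9 is the nearest thing to such a list in the text of the protocol. On the 24-hour aliquots it asks for two assays of albumin. The comparison that the study needs is two assays of total protein.

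A wrong analyte in a batch instruction does not affect single women at random. It affects every aliquot in the batch. Aliquots are limited, and the protocol gives no volume, so it cannot be judged from the document whether a batch run for the wrong analyte could be repeated.

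What is at stake is objective 3. A secondary matter is that the analysis and the economic evaluation both use laboratory SACr, while section 9 does not place that test in the sample flow.

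**Working it through.** No arithmetic applies: the point depends on no error rate, power, prevalence or sample size, and the plan gives no figure to reproduce. The check sets the sections side by side.

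| Question | Sections 6 and 8 | Section 9 |
|---|---|---|
| Analyte of the central two-assay analysis | Total protein (8.2); proteinuria (objective 3) | Albumin |
| Methods named for it | Benzethonium chloride and pyrogallol red (8.2) | None |
| Laboratory SACr | Index test, with analyser and assay type; no sample, laboratory or time (8.1) | Not mentioned, not excluded |

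1. **Could section 9 mean a separate, legitimate albumin comparison?** The heading of section 8.2 names 24-hour albuminuria as a comparative test, so measuring albumin is planned. But the only laboratory albumin method described anywhere is the immunoturbidimetric assay in section 8.1. A pair of albumin assays corresponds to nothing else in the protocol. The only pair of assays described for the secondary laboratory is the total-protein pair in section 8.2.

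2. **Could section 9 as written still deliver objective 3?** It would need total protein on the 24-hour urine by at least two methods. Section 9 provides a local 24-hour measurement and no central protein measurement. Section 8.1 says that urinary protein is measured by benzethonium chloride in all recruiting hospitals. The local results would then give one method, and pyrogallol red would be absent. The central benzethonium chloride result, which section 8.2 wants for inter-laboratory variation, is not in section 9 either.

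3. **Does the analysis section rescue it?** Section 12.2 allows for sites with different 24-hour assays and would stratify by assay type. That does not fit the single method in section 8.1. Even if some sites did use another method, the comparison would be between different women at different hospitals. It would not be two methods applied to the same urine, which central testing of stored aliquots makes possible.

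4. **Is laboratory SACr needed?** Yes. Section 12.2 compares laboratory quantitative SPCr and SACr with the other tests by areas under ROC curves, and section 12.3.1 has dipstick plus laboratory SACr as an economic option separate from dipstick plus point-of-care SACr. Section 8.1 commits to the test but does not say which sample it uses or where it is run, and section 9 does not fill that gap.

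**The case against.** The strongest defence is that section 8.2 is as much part of the protocol as section 9. It assigns the benzethonium chloride assay to the secondary laboratory and adds pyrogallol red, so a laboratory that reads the whole document would know what to run. The word for albumin in section 9 may be a slip. This stands as far as it goes: the data would be lost only if section 9 alone were followed. It does not remove the contradiction, because the two sections give different instructions for the same aliquots and nothing says which prevails.

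A reader might also infer stronger conclusions that the documents do not support.

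- **That objective 1 cannot be met.** Objective 1 is "To evaluate the diagnostic accuracy of quantitative assessments of SPCr and SACr (index tests) at different thresholds in predicting severe PE". Laboratory SPCr is in the section 9 workflow, and so is a fully quantitative point-of-care SACr. Objective 4 separates quantitative from point-of-care assessments, so laboratory SACr is probably intended. Its absence from section 9 is still a gap in description and not a failure of the objective.
- **That laboratory SACr is never scheduled, or would be available for none of the samples.** Sections 8.1, 12.2 and 12.3.1 all count on it, section 9 does not rule it out, and a spot aliquot is frozen on which it could be run. Figure 1 (study design) and Figure 2 (patient flow) are not shown and may list further tests.
- **That the point-of-care lists contradict each other.** Section 8.1 describes only "Point of Care tests (Semi quantitative reagent strip SACr)", while section 9 lists three tests. Section 5.2 already describes all three, so section 8.1 is incomplete and not in conflict.

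**Conclusion.** The contradiction on the analyte holds. Section 9 gives the secondary laboratory's two-assay analysis to albumin; section 8.2 and objective 3 require it for total protein. If section 9 alone governed the laboratory work, the pyrogallol red total-protein data for objective 3 would be missing, and local results would not replace them.

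The size is one secondary objective, conditional on which section is followed. No percentage of lost data can be given. The primary objective is not shown to be at risk.

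The conclusion rests on three assumptions: that the single protein method in section 8.1 covers the local 24-hour measurements as well as the spot urine; that the albumin method in section 8.1 is the only one planned; and that the figures not shown do not override the text. A correct flow chart could lower the practical risk, but the wording of section 9 would still disagree with section 8.2.

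The missing sample and laboratory for laboratory SACr are a secondary clarification.

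**What to change.** 1. In section 9, state that the 24-hour aliquots are analysed in the secondary laboratory for total protein by both benzethonium chloride and pyrogallol red, as section 8.2 plans.
2. State separately how 24-hour albumin is measured, including how many assays are used. It is a named comparative test and should stay, but the number of albumin assays should be confirmed by the study team and not assumed.
3. In section 9, state on which sample and in which laboratory the laboratory SACr of section 8.1 is run.
4. Check that Figures 1 and 2 and the laboratory request form agree with the amended text. Section 12.1 refers to a preliminary analysis of the first 1200 women recruited, so also check which tests were requested for any batches already sent.

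The cost is protocol wording and the request form. No further women or samples are needed, and the two total-protein assays and laboratory SACr are already planned in section 8.

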9.1 Selection of study participants

9.1.1 Setting

The trial will be conducted in up to 36 obstetric units in the UK, with an average of 70 women being recruited each month across all centres.

[figure not shown]
9.1.2 Inclusion criteria

Pregnant women aged between 16 and 45 years old who are more than 20 weeks gestation with confirmed gestational hypertension (systolic BP \geq 140 mmHg and/or diastolic BP \geq 90 mmHg) and trace or more proteinuria on automated dipstick urinalysis. This is below the threshold of 1+ considered “test positive” by NICE [5] and will thus allow exploration of the lower threshold for the index tests, i.e. below 300 mg/l protein.

9.1.3 Exclusion criteria

Exclusion criteria: Women with gestational hypertension but no proteinuria on automated dipstick urinalysis, sustained proteinuria from before 20 weeks gestation, pre-existing renal disease, pre-gestational diabetes and chronic hypertension.

Figure 2: Study Patient Flow and Clinical Care

10. ETHICS

10.1 Declaration of Helsinki

The Investigator will ensure that this study is conducted in full conformity with the current revision of the Declaration of Helsinki (last amended October 2000, with additional footnotes added in 2002 and 2004).

10.2 Guidelines for Good Clinical Practice (GCP)

The Investigator will ensure that this study is conducted in full conformity with The European Union Clinical Trials Directive, which requires clinical trials to be conducted according to the principles of Good Clinical Practice (GCP) and was implemented into UK Statute by the Medicines for Human Use (Clinical Trials) Amendment Regulations 2006.

10.3 Obtaining informed consent

A patient information leaflet (PIS) will be given to all women at the time of booking for antenatal care by the community and clinic midwives. The leaflet will also be made generally available and prominently displayed in various areas within the participating hospitals and their community antenatal clinics. The leaflets will also be translated into minority languages (Polish and Urdu) and made available on the internet. The information will detail the exact nature of the study and the implications of participation in the study. It will be clearly stated that the woman is free to withdraw from the study at any time and for any reason without prejudice to future care, with no obligation to give the reason for withdrawal. All women will have the opportunity to ask questions about the study and to have their questions answered.

10.4 Withdrawal criteria

In accordance with the current revision of the Declaration of Helsinki (amended October 2000, with additional footnotes added in 2002 and 2004), women have the right to withdraw both herself and her baby from the study at any time and for any reason, without prejudice to their future medical care. She is not obliged to give any reason for this. Should this happen the women will be informed that the data already collected will be used for study purposes.

10.5 Independent Ethics Committee

A copy of the protocol, proposed consent form, and written participant information and any proposed advertising material will be submitted to an Independent Ethics Committee for written approval. The Chief Investigator will submit and, where necessary, obtain approval from the Independent Ethics Committee for all subsequent protocol amendments and changes to the informed consent documents. The Investigator will notify deviations from the protocol to the Independent Ethics Committee in accordance with local procedures.

10.6 Participant confidentiality

The Chief Investigator will ensure that all information about the mother and baby is kept confidential. The mother and baby will be identified by name (consent will have been given by the parents) and unique study number on the data collection forms. This information will be collected with the parent(s) consent to enable 6 week follow-up to be undertaken. All documents will be stored securely and kept in strict confidence in compliance with Data Protection Act (1998).

11. ADVERSE EVENT MONITORING AND REPORTING

11.1 Expected Serious Adverse Events (SAE's)

The following are adverse events that could reasonably be expected for this group of mothers and babies during the course of the Study and do not require immediate reporting:

- Eclampsia
- Maternal admission to HDU/ITU
- Admission to NICU
- Stillbirth / Neonatal Death
- Maternal Death

11.2 Serious (unexpected) adverse event (SAE) reporting procedures

All expected SAE's will be reported on the data collection forms and will be reviewed by the Project Management Group (PMG) at the end of the pilot study. If any of the serious adverse events listed above occur they will be reported to the Oversight Committee (OC) as described and will also be reviewed by the PMG at the end of the pilot study.

11.3 Evaluation of AEs and SAEs

Seriousness, causality, severity and expectedness should be evaluated by the PMG. As this study is observational and does not involve a change in clinical practice all such events will also have been referred to the units Risk Management group and have been reviewed clinically.

Assessment of Seriousness

The Investigator should make an assessment of seriousness using standard definitions in Appendix two.

Assessment of Causality

The Investigator must make an assessment of whether the AE/SAE is likely to be related to false negative results from proteinuria testing according to the following definitions.

Unrelated: where an event is not considered to be related to the Study test.

Possibly: although a relationship to the Study test cannot be completely ruled out, the nature of the event, the underlying disease, concomitant medication or temporal relationship make other explanations possible.

Probably: the temporal relationship and absence of a more likely explanation suggest the event could be related to the Study test.

Definitely: the test result was directly related to the AE/SAE.

Given that clinical protocols are not being altered by this study and that it is already accepted that all proteinuria tests have false negative results it is unlikely that such assessments will result in stopping the study unless there is a clear over expression of AE/SAE with particular test results. Alternative causes, such as natural history of the underlying disease, other risk factors and the temporal relationship of the event to the treatment, should be considered and investigated.

Assessment of Expectedness

If an event is judged to be an AR/SAR, the evaluation of expectedness should be made based on knowledge of the event and the relevant results.

11.4 Reporting of SAEs/SARs/SUSARs

Once the Investigator becomes aware that an SAE has occurred in a study participant, they must report the information to the Study Office within 24 hours. The SAE form must be completed as thoroughly as possible with all available details of the event. If the Investigator does not have all information regarding an SAE, they should not wait for this additional information before recording the SAE information.

The SAE report must provide an assessment of causality and expectedness at the time of the initial report to the Study Office, detailing Assessment of Causality and Assessment of Expectedness as described above.

The Study Office will notify the Sponsors and the CI of all events reported for assessment, via fax.

**Contact details for reporting SAE(s)
Please send SAE Form(s) via [contact],
Attention NCTU DAPPA Trial Manager**

All unexpected SAE's must be reported to the CI within one working day of discovery or notification of the event. A Standard Operating Procedure (SOP) outlining the reporting procedure for clinicians will be provided on the reverse of the SAE form. An SOP will also be available as part of the Study specific SOPs, which will outline the reporting procedure at the Study Office. All SAE information must be recorded on an SAE form and faxed to the CI if necessary. Additional information received for a case (follow-up or corrections to the original case) need to be detailed on a new SAE form.

The CI will report all suspected adverse reactions, which are both serious and unexpected (SUSAR/SAE's), to the Competent Authorities (MHRA) and Ethics Committee concerned. Fatal or life-threatening SUSARs must be reported within 7 days and all other SUSARs within 15 days.

In addition to the expedited reporting above, the CI shall submit, once a year, or on request, a safety report to the Competent Authority.

